Official Title: Aspirin as Adjuvant Therapy in Young Psychotic Patients NCT number: NCT02685748

Study Protocol and Statistical Analysis Plan

Effect of adjuvant aspirin therapy on neurological soft signs and PANSS in young psychotic patients

A randomized, interventional, double-blind, placebo-controlled clinical trial

Protocol name:	Aspirin2016.2
Date:	25 October 2016.
Donor:	Stanley Medical Research Institute, [name], [name] 20815, SAD
Sponsor:	Clinic for Mental Diseases "[name]", [name], Serbia
Principal Investigator, Grant Holder:	MD [name], psychiatrist
Co-investigators:	MD/PhD [name], neuropsychiatrist MD [name], psychiatrist MD [name], psychiatrist

Background:

The clinical trial team would conduct a randomized, interventional, double-blind, placebo-controlled study in two parallel groups of patients who were neuroleptically naive or previously minimally medicated (who did not take antipsychotics during the previous 6 months) with the illness duration of up to seven years. Patients of both sexes, ages 18 to 28, would participate in the trial, in accordance with the tenth revision of the International Classification of Diseases (ICD10), they would meet the diagnostic criteria for the illnesses ranging from F 20 to F 29. After meeting the inclusion and exclusion criteria and having signed an informed consent form, the patients would be randomized into two groups:

Experimental group - EG: antipsychotic + Aspirin

and

Control group – CG: antipsychotic + placebo.

The EG patients would be administered 1000 mg aspirin pro die with gastric protection pantoprazole 40 mg pro die, both medicines in two doses during 6 weeks of hospital treatment at Clinic form Mental Disorders "[name]". The trial would last for 18 months and would include the total of 100 to 120 patients.

Objective and hypotheses:

The objective of the trial would be to determine the effect of adjuvant aspirin therapy on neurological soft signs, positive and negative syndrome in schizophrenia, cognition, inflammatory factors and cytokine profile.

Working hypotheses:

- 1. Changes in PANSS and MoCA scores as well as inflammation factors in both patient groups, more in the experimental group.
- 2. Changes in the cytokine profile in both patient groups.

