- 3. In case of significant change of SNS and cytokine profile in the experimental group the results would support the cytokine hypothesis. If there were no significant changes in the SNS in the experimental group, the results would support the SNS as a trait of schizophrenia.

Clinical Trial Design:

A randomized, interventional, double-blind, placebo-controlled clinical trial in two parallel groups of patients who were neuroleptically naive or previously minimally medicated (who did not take antipsychotics during the previous 6 months) with the illness duration of up to seven years. Patients of both sexes, ages 18 to 28, would participate in the trial, in accordance with the tenth revision of the International Classification of Diseases, would meet the diagnostic criteria for the illnesses ranging from F20 to F29. Upon fulfilment of inclusion and exclusion criteria and signed Informed consent form, they would be randomized in two groups: experimental (EG) and control group (CG). Patients belonging to the control group would be administered antipsychotic therapy and placebo, whereas patients in the experimental group would be administered regular antipsychotic therapy and aspirin. EG patients would be administered 1000 mg aspirin pro die with gastric protection- pantoprazole 40 mg pro die, both medicines in two doses in duration of 6 weeks.

A software application specialized in the randomization of subjects for clinical trials -*Sealed Envelope* - will be used for randomization. The obtained list will be in possession of one co-investigator and only he or she will know which group the patient belongs to. Only upon completion of the trial, after taking the serum samples from the last patient, and cytokine profile analysis (cytokine profile analysis would be performed at the end of the trial, after the serum sample from the last patient was taken at both test times) would the patient's belonging to the EG or CG group be revealed.

The co-investigator in charge of randomization would give out the medicine boxes and the medicines would all look identical - packed in the same capsules for overcapsulation by the company **Capsugel**. Placebo tablets would be manufactured by Galenika A.D. The patient would be administered Bayer's Aspirin tbl. á 500 mg and Nolpaza tbl. á 20 mg produced by Krka-Farma D.O.O.

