Three visits are planned. The first visit after admission to the Clinic. If the patient fulfils the inclusion criteria and none of the exclusion criteria (anamnestic data, somatic and psychiatric examination), and after the Informed consent form has been signed, PANSS scale test and blood sample would be taken for laboratory analysis. Laboratory analysis would be complete blood count (RBC, WBC, PTC, Hgb, Hct), sedimentation, C reactive protein, blood biochemical analysis (glycaemia, cholesterol, triglycerides, transaminases, CK, bilirubin, uric acid, creatinine, urea), and electrolytes (Na, K). Th1, Th2 and Th17 cytokines would be subject to the immunological assays. Each patient would be given an identification number (from one upwards) and the tubes with serum for the cytokine profile would be labelled with the same number, in terms of x/y, where x is the patient's identification number and y- may be "1" or "2" ("a" or "b"), where "1" or "a" would mean the first blood draw (at the beginning of the trial) and the number "2" or "b" - the second blood draw (at the very end of the trial).

After calming down of the acute signs of psychosis, between the third and fifth day of hospitalization, the second visit would be made when testing of the neurological soft signs would be performed according the Heidelberg Soft Neurological Signs Scale, the MoCA Cognitive Assessment Scale, and then the patient would be randomized to an experimental or control group if he/she meets the inclusion and no-exclusion criteria, if there are no somatic contraindications (with a stable ECG), and if he/she still wishes to participate in the trial.

The staff of the ward where the patient would be accommodated would be given two boxes of medicines labelled "Clinical Trial Medication 1" and "Clinical Trial Medication 2" that would be administered to patients – one medicine from each box, in the morning and in the evening.

After 6 weeks from the second visit (+/- 3 days), the third visit would be made when the patient would be examined, the PANSS, MoCA and Heidelberg scales testing repeated, and the blood sample taken again for laboratory analyses - inflammatory factors and cytokine profiles.

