Continuous variables will be displayed descriptively using the minimum and maximum values, mean values and standard deviation. Categorical variables will be presented descriptively using absolute and relative frequency as well as graphically using a pie chart.

Kolmogorov-Smirnov or Shapiro-Wilk test, depending on sample size, will be used to check the normality of data distribution, as well as graphical method of using histogram. If the data follow the normal distribution, parametric tests will be used for the statistical analysis of the data; otherwise the corresponding non-parametric tests will be used.

For the analysis of significant continuous variables over time, the Paired Samples t Test will be used if the data follow a normal distribution or the Wilcoxon test if the data do not follow the normal distribution. Significant results will be presented graphically using a bar chart or boxplot.

For the analysis of significant difference of continuous variables between the control and experimental groups, the Independent Samples t Test will be used if the data follow a normal distribution or the Mann-Whitney test if the data do not follow the normal distribution. Significant results will be presented graphically using a bar chart or boxplot.

For the analysis of the dependence between two continuous variables, the value of Pearson's or Spirman's correlation coefficient will be interpreted. In the case of strong correlations, the dependence will be shown both by the regression equation and graphically using the scatterplot.

For the analysis of the dependence between the two categorical variables, a Chi-squared test, that is, a Fisher's exact-dependency test will be used. The results will be presented graphically using a bar cluster graph.

The results will be considered statistically significant if the p value is less than 0.05.

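### Hypothesis 3 reads a non-significant SNS change in the aspirin arm alone as support for SNS being a trait, which non-significance cannot show and the control arm could contradict

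*Combined protocol and SAP*

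**What the plan says.** The rule is the second sentence of item 3 under Working hypotheses: "If there were no significant changes in the SNS in the experimental group, the results would support the SNS as a trait of schizophrenia". The first sentence has the same form and also names only the experimental group (EG): "In case of significant change of SNS and cytokine profile in the experimental group the results would support the cytokine hypothesis".

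The Statistical analysis plan supplies the threshold: "The results will be considered statistically significant if the p value is less than 0.05". For change over time, "the Paired Samples t Test will be used if the data follow a normal distribution or the Wilcoxon test" is listed. For the comparison of arms: "For the analysis of significant difference of continuous variables between the control and experimental groups, the Independent Samples t Test will be used". Neither test is assigned to hypothesis 3. The between-group test is not said to apply to the week-6 score or to the change.

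Under Clinical Trial Design, the Heidelberg scale is scored at visit 2, before randomisation, and again at visit 3 about six weeks later. Visit 2 takes place "After calming down of the acute signs of psychosis, between the third and fifth day of hospitalization". PANSS is scored at visits 1 and 3. For the control group (CG): "Patients belonging to the control group would be administered antipsychotic therapy and placebo". The Background says the trial "would include the total of 100 to 120 patients". The documents give no derivation of that number, and no allocation ratio, SNS effect size, SD, power or margin.

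**The concern.** There are two faults in the inference.

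1. A p value of 0.05 or more does not show stability. Without a margin or an interval criterion, a flat SNS course and an imprecisely estimated change lead to the same conclusion. The fewer evaluable patients in EG, the more likely the trait reading becomes.

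2. The rule looks at one arm. Whether SNS stays fixed while treated psychosis resolves is a question for both arms, since both receive antipsychotics. If SNS changed in CG but not significantly in EG, the sentence would still yield trait. If SNS stayed flat in EG and worsened in CG, a possible aspirin effect would also be reported as trait.

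SNS is named in the trial title and in the objective, so a reader will take this conclusion seriously.

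**Working it through.** **No plan figure to reproduce.** The total of 100 to 120 has no stated derivation.

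**Inputs.** From the documents: total 100 to 120 (Background); threshold 0.05 and a paired test over time (Statistical analysis plan). Assumed: 1:1 allocation, so n = 50 to 60 in EG; two-sided testing; normally distributed change; no drop-out. Assumed true changes: d = 0.2 to 0.5, in SDs of the within-patient change.

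**Chance of the trait reading although SNS truly changes.** For a paired t-test with noncentrality δ = d√n and n − 1 degrees of freedom,

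P(trait reading) = F(t_crit; n−1, δ) − F(−t_crit; n−1, δ),

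where F is the noncentral t distribution function. Example: n = 50, d = 0.3 gives δ = 0.3 × √50 = 2.12, t_crit = 2.010 and P = 0.452.

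| True change (SD of change) | n = 50 | n = 60 | n = 40 (illustrative loss) |
|---|---|---|---|
| 0.2 | 0.716 | 0.668 | 0.765 |
| 0.3 | 0.452 | 0.372 | 0.543 |
| 0.4 | 0.208 | 0.138 | 0.306 |
| 0.5 | 0.066 | 0.032 | 0.131 |

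The last column matters because, under Criteria for Trial Termination, patients may leave voluntarily and those with aspirin side effects are excluded. No loss rate is stated, so 40 is only an example.

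**If the sentence is read as a between-arm test instead.** With an independent t-test and δ = d√(n/2), the chance of non-significance at 50 / 60 per arm is 83% / 81% for 0.2 SD, 68% / 63% for 0.3, 49% / 42% for 0.4 and 30% / 23% for 0.5. The difficulty grows on this reading.

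**Conflict with the control arm.** Suppose both arms share the same true change of 0.3 SD. The arms are independent, so the chance that EG is non-significant while CG is significant is

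- n = 50 per arm: 0.452 × (1 − 0.452) = 0.248
- n = 60 per arm: 0.372 × (1 − 0.372) = 0.234

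In about one trial in four, the rule would give trait while the placebo arm showed a significant SNS change.

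**What an interval-based rule can deliver.** The 95% CI half-width, in SDs of change, is t_crit/√n:

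- EG alone: 2.010/√50 = 0.28; 2.001/√60 = 0.26
- both arms pooled: 0.20 (n = 100); 0.18 (n = 120)

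Take a true change of zero in both arms and an illustrative margin of 0.3 SD. By simulation, the 95% CI then lies wholly inside the margin in 69% (n = 100) to 81% (n = 120) of trials when pooled, but in only 12% (n = 50) to 26% (n = 60) in a single arm. The criterion must therefore say which interval it uses.

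**The case against.** The best defence is that this is a working hypothesis, phrased as support, and that the SAP contains no step that outputs a trait verdict. The other hypotheses do not depend on it. The SAP also lists tests over time, tests between groups and correlations, so control-arm change and SNS against PANSS can be examined with the planned methods. All of this is true. It limits the point to the inference rule and does not rescue the rule: no listed test is tied to hypothesis 3, and support still needs more than a non-significant p value.

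Four stronger readings are tempting, and the documents do not bear them out:

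- *The plan ignores the control arm.* It is missing from this rule, not from the SAP.
- *The trial is underpowered for SNS.* This is not shown. At 0.4 SD the paired test has 79% (n = 50) to 86% (n = 60) power, and whether 0.2 or 0.3 SD matters clinically is not stated.
- *A flat EG shows only that aspirin failed.* EG also receives antipsychotics, so a flat SNS course during treatment does bear on trait versus state. Only a null difference between arms is limited to the aspirin question.
- *The day 3 to 5 baseline biases the rule towards no change.* That would require SNS to move in those first days, and the documents have no data on this. The timing limits what can be claimed; it is not a demonstrated bias.

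**Conclusion.** The second sentence of hypothesis 3 is wrong as written. It draws a positive conclusion from non-significance in one arm, with no margin or interval. Under the assumptions above, a true change of 0.3 SD would be read as trait in 45% (n = 50) to 37% (n = 60) of trials. The range runs from 72% at 0.2 SD with n = 50 to 14% at 0.4 SD with n = 60, and loss of patients from EG raises every figure. These percentages depend on assumed effect sizes, allocation and sidedness. The logical fault does not: it remains at any sample size until the smallest relevant SNS change is stated.

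**What to change.** Replace the second sentence of hypothesis 3, with a matching line in the SAP:

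> A non-significant SNS change in the experimental group is inconclusive. SNS change from visit 2 to visit 3 will be reported with 95% CIs in all randomised patients pooled and in each arm. Support for SNS stability will be claimed only if the pooled 95% CI lies inside a Heidelberg margin fixed before unblinding; the per-arm CIs are descriptive. The aspirin-minus-placebo difference in SNS change will be reported with its 95% CI, and a null difference means only that no aspirin effect on SNS was demonstrated.

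Add two limits on interpretation. Stability applies only from visit 2 (day 3 to 5) onward. PANSS change covers visits 1 to 3, so it is not the same interval as SNS change, and PANSS improvement before visit 2 must not be set against SNS change after it.

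Pooled change can be computed without the allocation list, so the margin should also be fixed before any visit 3 Heidelberg data are summarised. The per-arm intervals should be read alongside the pooled one, because opposite changes in the two arms could cancel.

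Cost: one reworded hypothesis, one SAP line and a justified margin, with no new data. The downside is that the result can now be inconclusive. With the illustrative 0.3 SD margin and no true change, that would happen in about 19% to 31% of trials (100% minus 81% and 69%).

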Control laboratory analyses would be performed on each patient on days 14th and 28th from the second visit. If patients received high dose valproic acid in therapy, valproatemia control would be performed, and if they received antidepressants from the SSRI group, bleeding time would be controlled.

Serums administered to patients would be transported in a cold chain to the Centre for Molecular Medicine and Stem Cell Research at the Faculty of Medical Sciences, University of Kragujevac, where they would be stored at -70°C until analyses were performed.

Criteria for Trial Termination:

The criteria for trial termination for individual subjects, parts of the trial or the whole trial would be defined as follows: the subject may voluntarily leave the trial at any moment. In the event that side effects of adjuvant aspirin therapy occur, the patient would be excluded from the trial. Occurrence of bleeding from the nose or gums, bruising, bleeding in the GIT or brain, and confusion, anaphylactic reactions or acute renal failure would imply the immediate exclusion of subjects from the trial. If there is an increase in valproatemia (in patients taking valproic acid in therapy) - the dose of the medicine would be excluded from the trial. The entire trial would be discontinued by the emergence of a large number of complicated side effects, as well as by compromising drug storage.

Selection and inclusion of subjects:

Inclusion criteria:

- Age 18 to 28
- Diagnostic categories from F 20 to F 29
- Illness duration \leq 7 years

> Exclusion criteria:

- PAS abuse
- Primary cognitive impairment
- Contraindications and special caution for acetylsalicylic acid and pantoprazole:
 - Hypersensitivity to acetylsalicylic acid and other NSAIDs (possible cross-reaction)
 - Gastric ulcer and/or duodenum ulcer, gastritis
 - Pregnancy
 - Haemophilia, bleeding disorders
 - Gout

- Asthma, COPD, NSAID-induced bronchospasm
- Angioedema, urticaria
- Haemolytic anaemia
- Use of warfarin, methotrexate
- Diabetes
- Decreased liver and / or kidney function
- Heart failure
- Surgical/dental intervention
- Interactions with specific psycho-pharmaceuticals
- Sensitivity to pantoprazole

Statistical analysis plan:

Statistical data analysis will be done in the programme IBM SPSS Statistics v.20.

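### Pregnancy is an exclusion, but nothing in the stated screening can detect an unrecognised or unreported early pregnancy before randomisation

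*Combined protocol and SAP*

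**What the plan says.** The Background section sets the population: "Patients of both sexes, ages 18 to 28, would participate in the trial". Pregnancy appears once in the document, as an exclusion in Selection and inclusion of subjects, among the contraindications to and cautions for aspirin and pantoprazole.

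Clinical Trial Design describes screening in two steps.

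- **Visit 1, after admission.** Eligibility is judged as follows: "If the patient fulfils the inclusion criteria and none of the exclusion criteria (anamnestic data, somatic and psychiatric examination". Blood is then taken, once consent has been signed. The panel is itemised: "Laboratory analysis would be complete blood count (RBC, WBC, PTC, Hgb, Hct), sedimentation, C reactive protein", then "blood biochemical analysis (glycaemia, cholesterol, triglycerides, transaminases, CK, bilirubin, uric acid, creatinine, urea), and electrolytes (Na, K". For the immunology, "Th1, Th2 and Th17 cytokines would be subject to the immunological assays".
- **Visit 2, on hospital day 3 to 5, once acute symptoms have settled.** The patient is randomised "if he/she meets the inclusion and no-exclusion criteria, if there are no somatic contraindications (with a stable ECG") and if still willing to take part.

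After randomisation, "Control laboratory analyses would be performed on each patient on days 14th and 28th from the second visit". The content of these later analyses is not listed. Two further tests are named, valproate level and bleeding time, and each depends on co-medication.

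**The concern.** An exclusion protects patients only if some step before randomisation can identify those it covers. Here the sponsor has decided that pregnant women should not enter, and the age range makes pregnancy a realistic possibility. Yet the procedures described before randomisation rest on what the patient says and what an examination shows. An early pregnancy may be unknown to the patient, or known and not mentioned.

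What is at stake is safety. A woman whom the plan means to keep out could be allocated to the experimental group and receive aspirin and pantoprazole for 6 weeks. The plan also does not say what happens if a pregnancy comes to light during treatment, because Criteria for Trial Termination does not mention it.

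**Working it through.** **Text check.** The plan states no figure on this point, so there is none to reproduce. The check is whether any listed step can detect a pregnancy that the patient does not report.

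| Step | What is listed | Can it detect an unreported early pregnancy? |
|---|---|---|
| Visit 1 eligibility | History, physical and psychiatric examination | Not reliably; history finds only what is known and reported |
| Visit 1 laboratory | Blood count, sedimentation, CRP, biochemistry, electrolytes, cytokines | No |
| Visit 2 re-check | Criteria re-applied, stable ECG | No test for it is named |
| Days 14 and 28 | Laboratory checks, not itemised | Too late; the patient is already randomised |

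A search of the whole document finds no mention of a pregnancy test, hCG or contraception. The consent pages were removed from the supplied text and could not be checked.

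Several other exclusions do have a related analyte in the panel: glucose for diabetes; transaminases, bilirubin, creatinine and urea for liver and kidney function; uric acid for gout. Pregnancy has none.

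**Illustrative size.** Inputs:

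- Total patients: 100 to 120 (Background).
- Share of women: one half. Assumption, giving n = 50 to 60.
- Share of those women unknowingly pregnant at admission: p = 0.5% to 3%. Assumption.
- Allocation: 1:1. Assumption; the ratio is not stated.

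Both arms together:

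- Expected number = n × p: 50 × 0.005 = 0.25, and 60 × 0.03 = 1.8.
- Chance of at least one = 1 − (1 − p)^n: 1 − 0.995^50 = 0.222, and 1 − 0.97^60 = 0.839.

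The plan gives aspirin only to the experimental group, so the number exposed to it is half of this:

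- Expected number = n × p/2: 0.25/2 = 0.125, and 1.8/2 = 0.9.
- Chance of at least one = 1 − (1 − p/2)^n: 1 − 0.9975^50 ≈ 0.12, and 1 − 0.985^60 ≈ 0.60.

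**The case against.** The best defence is that this is a short protocol which does not spell out every procedure. The ECG shows this: it is needed for randomisation but is not among the visit-1 procedures. Pregnancy is also not the only exclusion without a matching test. Substance abuse has no toxicology screen, and bleeding disorders have no coagulation assay at screening. On this view the document leaves verification to the clinic, which may test women on admission as routine.

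That defence stands in part. Silence does not prove that no test would be done, and a reader should not infer that it does. It shows that the plan, followed as written, does not require one. Gaps for other exclusions do not close this one.

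A reader might also infer that:

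- **Any early pregnancy would pass.** It would not. A known and reported pregnancy is caught by history.
- **Eligibility rests only on a history taken in acute psychosis.** The criteria are re-applied at visit 2, when the patient is calmer and before trial medication starts. Retaking the history then helps with unreported pregnancies, but not with unrecognised ones.
- **The plan lists every laboratory test, so the omission is deliberate.** Only the visit-1 panel is itemised; the day 14 and day 28 checks are not.
- **A pregnancy found later would force withdrawal and cost the trial a patient.** The termination criteria do not say so.

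**Conclusion.** The point holds in limited form. The plan excludes pregnancy and admits women aged 18 to 28, but none of its stated steps before randomisation can detect an unrecognised or unreported early pregnancy. Such a patient could be randomised. This conclusion comes from reading the eligibility criteria against the visit procedures and depends on no numerical assumption.

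The size is uncertain. Under the assumptions shown, 0.125 to 0.9 women would be exposed to aspirin, with a chance of at least one of about 12% to 60%. The share of women, the prevalence and the allocation ratio all lack a source in the documents, so the range shows only that the event is neither negligible nor certain. The tempting figure of 22% to 84% should not be read as the risk of aspirin exposure, since it counts both arms and controls receive placebo.

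This is a minor, inexpensive safety improvement. It has no bearing on the sample size, the outcome measures or the statistical tests.

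**What to change.** Reconcile Selection and inclusion of subjects with Clinical Trial Design, so that the plan states how and when the pregnancy exclusion is verified. In practice:

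- add a pregnancy assay for women to the visit-1 laboratory list, run on the blood already drawn;
- state that the result must be available when the exclusion criteria are re-checked at visit 2, before randomisation.

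If the clinic already tests women on admission, one sentence saying so, and requiring the result at visit 2, is enough.

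The cost is one assay per woman, so 50 to 60 assays if half the patients are women. The documents give no price. No extra visit or blood draw is needed, because visit 1 already includes a sample and randomisation waits until hospital day 3 to 5. Treatment, design and analysis are unchanged.

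### If one MoCA form is used at both visits, a practice gain alone can appear to confirm the hypothesis 1 claim that MoCA changes in both groups

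*Combined protocol and SAP*

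**What the plan says.** Under Clinical Trial Design, the baseline MoCA falls at the second visit, directly before allocation: "the MoCA Cognitive Assessment Scale, and then the patient would be randomized". The retest interval is fixed: "After 6 weeks from the second visit (+/- 3 days), the third visit would be made". At that third visit the plan has "the PANSS, MoCA and Heidelberg scales testing repeated". No section mentions a version, an alternate form, a familiarisation session or a correction for retesting.

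Under Objective and hypotheses, the first working hypothesis reads "Changes in PANSS and MoCA scores as well as inflammation factors in both patient groups, more in the experimental group". It has two parts: change within each group, and a larger change with aspirin.

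The Statistical analysis plan gives a separate test for each kind of question. For change over time: "For the analysis of significant continuous variables over time, the Paired Samples t Test will be used", with the Wilcoxon test as the non-normal alternative. For the comparison of groups, "the Independent Samples t Test will be used if the data follow a normal distribution", with Mann-Whitney as the alternative. It does not say whether the group comparison uses change scores or final scores. The threshold is common to all tests: "The results will be considered statistically significant if the p value is less than 0.05".

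**The concern.** The MoCA is scored on what the patient does, so a patient who has met the items before may do better the second time without any cognitive change. In most placebo-controlled trials this matters little, because practice is shared by the arms and cancels in their difference. Here the plan also makes change within each arm a hypothesis in its own right, and the paired test compares that change with zero. It cannot separate learning from improvement. Both arms receive antipsychotics and there is no retest-only group, so nothing else in the design separates them either.

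At stake is a report that cognition improved in both groups when it did not. Cognition is one of the stated objectives. If one form has been given twice, later analysis cannot recover the practice component.

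**Working it through.** **Inputs from the documents.** The total sample is 100 to 120 (Background). The significance level is 0.05 (Statistical analysis plan). There are two groups, with MoCA at the second and third visits. The plan states no power, effect size or SD, so it offers no figure of its own to reproduce.

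**Assumptions.** Allocation is 1:1 with no dropout, so n = 50 to 60 per arm. Tests are two-sided. The SD of within-patient MoCA change, s, is 2.5 to 3 points. The mean practice gain, g, is 0.5 or 1 point. True cognitive change is zero.

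**Step 1: how small a mean gain is significant.** The paired t test rejects when the observed mean change exceeds t(0.975, n−1) × s/√n. The multiplier of s is 0.284 for n = 50 and 0.258 for n = 60. The threshold therefore runs from 0.258 × 2.5 = 0.65 points to 0.284 × 3 = 0.85 points.

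**Step 2: chance that practice alone gives significance.** For one arm, this is the probability that a noncentral t variable with n−1 degrees of freedom and noncentrality (g/s)√n falls beyond ±t(0.975, n−1). The arms are independent, so the probability for both is the square.

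| g | s | n per arm | (g/s)√n | One arm | Both arms |
|---|---|---|---|---|---|
| 1.0 | 3 | 50 | 2.36 | 0.637 | 0.406 |
| 1.0 | 3 | 60 | 2.58 | 0.719 | 0.517 |
| 1.0 | 2.5 | 50 | 2.83 | 0.792 | 0.627 |
| 1.0 | 2.5 | 60 | 3.10 | 0.862 | 0.742 |
| 0.5 | 3 | 50 | 1.18 | 0.211 | 0.045 |
| 0.5 | 3 | 60 | 1.29 | 0.246 | 0.060 |
| 0.5 | 2.5 | 50 | 1.41 | 0.284 | 0.080 |
| 0.5 | 2.5 | 60 | 1.55 | 0.332 | 0.110 |

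With no practice gain the rates are 0.05 for one arm and 0.05² = 0.0025 for both.

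**Step 3: sensitivity to the assumptions.** Over a wider grid (gain 0.5 to 1.5, SD 2 to 4), the both-arm probability runs from 1.9% (gain 0.5, SD 4, n = 50) to over 99% (gain 1.5, SD 2). In SD units, it reaches 50% at a gain of 0.36 SD for n = 50 or 0.33 SD for n = 60.

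**Step 4: the comparison between arms.** With the same gain g in each arm, the expected difference in change is (g + aspirin effect) − g, which is the aspirin effect. A simulation of 20,000 trials per setting, with gains of 0.5 to 1.5, SD 2.5 to 3 and no aspirin effect, gave a rejection rate of 4.6% to 5.4% for the t test on change scores. Practice therefore leaves that test at its nominal level. In the same simulations, the experimental arm alone was significant in 0.5% to 23% of trials. Significant in one arm but not in the other is therefore not usable evidence for aspirin.

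**The case against.** The strongest reply is that the premise rests on silence. The sentence on the third visit names instruments, not forms, and repeating the MoCA with an alternate version would fit it. This stands: a reader might infer that the protocol prescribes the same form, and it does not. But an unqualified instruction to repeat a test is readily followed with the same sheet, and nothing in the plan prevents that.

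A second reply is that the trial asks about aspirin, and the randomised comparison answers that. This also stands. A reader might infer that practice undermines the part of hypothesis 1 that predicts more change with aspirin; Step 4 shows that it does not bias that test. The part predicting change in each group remains exposed.

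Third, the sizes depend on assumed inputs. They do, and at a gain of 0.5 points significance in both arms would be uncommon (4.5–11%), though still at least 18 times the nominal 0.25%.

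Fourth, parallel forms do not make a within-arm change attributable to treatment. Familiarity with the task remains, and the baseline is taken on days three to five of admission, so recovery from the acute episode is mixed in. This is correct, and it is why the fix has two parts.

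A reader might also infer that remembered items push scores towards the top of the scale and blunt the comparison between arms. The documents give no baseline MoCA level or spread, and the baseline follows shortly after acute psychosis, so they do not support that.

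**Conclusion.** The point holds in a limited form. If one form is used at both visits, practice alone can make the within-arm MoCA test significant and so appear to confirm that MoCA changes in both groups. With no true change, SD 2.5 to 3 and 50 to 60 per arm, the chance of significance in both arms is 41–74% for a 1-point gain and 4.5–11% for a 0.5-point gain. For one arm the corresponding ranges are 64–86% and 21–33%. Gain, SD, equal allocation, full follow-up and two-sided testing are all assumptions. The calculation is for the t test; the Wilcoxon alternative also compares change with zero and cannot separate practice from improvement either.

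The finding does not invalidate the aspirin comparison and does not change the sample size. It is a cheap improvement that has to be made before testing starts.

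**What to change.** 1. In Clinical Trial Design, state which MoCA form is given at each visit, and use different parallel forms at the second and third visits where equivalent forms exist in the patients' language. The documents do not show whether they do.
2. Balance form order within each arm, so that a difference in difficulty cancels from the mean change. The order must be known before the baseline MoCA, which precedes randomisation. One way is to fix the order beforehand and build it into the randomisation list as a stratum. Assigning it by odd or even identification number is simpler but balances the arms only on average.
3. In the Statistical analysis plan, label within-arm MoCA change as descriptive. Base any conclusion about aspirin and cognition on the between-arm difference in MoCA change, not on comparing the significance of two paired tests.

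The cost is a few sentences and obtaining a second form, with no extra visit or testing time. The downside is slightly more variance in the change scores if the forms differ in difficulty. If alternate forms are already intended, one sentence settles the first item, but the other two still apply.
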